#### *Storage of Study Data*

Study data will be kept in accordance with the Department of Veterans Affairs Record Control Schedule 10-1 (RCS 10-1). Storage and transfer of any Personally Identifiable Information (PII) or Protected Health Information (PHI) must be done in accordance with applicable VA and VHA policies and directives, state and federal regulations, and applicable statutes including the Health Insurance Portability and Accountability ACT (HIPAA). Unless explicitly requested and approved by data stewards, all sensitive patient data must remain on VINCI project servers and only aggregate data without PII / PHI may be transferred from VINCI. Any desired change in data storage location or transfer requires amending the original data request with an updated disposition of study data. The amendment must be approved by all data stewards before data may be transferred.

Violations of data policy or approved use of data will be subject to full penalty of law, which may include suspension of access privileges, reprimand, suspension from work, demotion, removal, and criminal and civil penalties.

Upon completion of the research project, the study principal investigator in conjunction with the VA Information Security Officer (ISO), and in accordance with VA policy, will ensure that, study data containing sensitive, confidential information will be returned to the VA, sanitized and removed from all servers, desktops, removable storage devices, etc.

#### *Data Access*

Only study team personnel explicitly authorized by data stewards will have access to project data. The study principal investigator has the responsibility for security of study. VINCI data managers and VA OI&T personnel not under the purview of the study principal investigator control the servers, network, processors, firewall and software in the VINCI environment, including access rights granted to study personnel.

When study personnel are no longer part of the research team, the study principal investigator will amend the data access request to terminate that person's access to all study data and notify the VA Information Security Officer of such action. No sensitive patient data may be shared with anyone who does not have a VA appointment. All study team personnel with access to sensitive patient data must stay current on required VA information security and privacy policy trainings.

#### *Data Storage Location*

Study data stored on VINCI servers is located at the Austin Information Technology Center, [name]. The specific server where the data are stored within the VINCI environment will be chosen by VINCI personnel. The server name and location within the Austin Information Technology Center may be changed at any time at the discretion of VINCI personnel.

#### *Specialized Software*

All software used to access sensitive patient data, whether provided by VINCI, or developed by the study team, will run in virtual desktop sessions on VINCI servers within the Austin Information Technology Center.”

## STATISTICAL ANALYSIS PLAN

### Overview

For this project, we plan to collect three major types of data assessed at times 1-3 (baseline/pre-intervention, 2 months/post-intervention, and 3 months follow up): community integration parameters including educational attainment and employment, individual characteristics such as PTSD; TBI self-efficacy, emotional status, coping, performance of real-world tasks, resilience and life satisfaction, and neuropsychological parameters including overall cognitive and executive functioning. Though we have removed the physical function assessments from future data collection, previously collected data on physical function may still be used for data analysis and subsequent publication and presentation purposes. The primary outcome will be the change in the three major types of parameters from pre- to post-intervention. Depending upon the hypothesis being tested (see Specific Aims section), participants will be stratified according to level of executive functioning, severity of conditions secondary to TBI (PTSD, level of functioning, emotional status), or degree of societal participation. Dependent variables will include TBI-self-efficacy, community integration indices, educational or work attainment as defined by the ICF qualifiers, and life satisfaction. Both objective (e.g. executive performance) and subjective (e.g., perceived TBI self-efficacy) data will then be obtained based on repeated measures over the three-year period. Multiple regression models will be fitted to explore continuous primary and secondary outcomes differentiating between groups at each time point and changes at the intra-individual and inter-individual levels over time. For categorical outcomes (e.g., low/high executive performance, or work status such as unemployed/employed, part-time/full-time), unconditional logistic and/or multinomial regression models will be implemented.

The basic testing of the hypotheses will involve ANOVA test and repeated measures ANOVA test. Bonferroni adjustments will be made to account for multiple testing.

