### **Power and sample size calculation**

110 participants with executive dysfunction due to diagnosed TBI will be randomized into the COMPASSgoal intervention or supported discharge groups, as assessed via the VHA TBI Comprehensive Evaluation screening tool. Participants in the supported discharge group will not receive the intervention, but will receive usual care provided by case managers with increased intensity of communication prompts. Participants in the intervention group will receive 8 goal self-management sessions over a period of approximately 10 weeks. We don't expect a significant change from post-intervention to 3 month post-intervention, the sample size calculations are based on a t-test for comparisons of mean change in the Community Reintegration of Service members (CRIS) subscale from pre- to post-intervention between two groups.

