### **Hypothesis:**

H0:  $\mu_1 = \mu_2$  where  $\mu_1$ = mean change in CRIS subscale from time 1 to time 2 in self-management group and  $\mu_2$ = mean change in CRIS subscale from time 1 to time 2 in supported discharge group  
H1:  $\mu_1 \neq \mu_2$

**Power Calculation:** PASS (Power Analysis and Sample Size Software, Kaysville, UT, 2008) was used for the power calculation. The primary outcome of this study is the frequency of social interactions measured via the Extent of Participation subscale of the CRIS. The power calculation was performed based on the hypothesis listed above by using a two-sided t-test with assumption of normality. The level of significance was set at 0.05 and power was set at 90%. The effect size and standard deviation used for the power calculation were estimated based on a previous VA study and clinical judgment. 44 subjects in each

[figure not shown]
group, for a total of 88 subjects will provide 90% power to test an effect size of 0.71 with a SD of 7 for difference in CRIS subscale score between groups with  $\alpha=0.05$  (two sided). After adjustment for 20% loss to follow-up, we will recruit 55 subjects in each group of this study, a total of 110 subjects.

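### The SAP makes change in three types of parameters primary, while the trial is sized on one CRIS subscale at 0.05; the Bonferroni rule has no stated family, number of tests or alpha

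*Combined protocol and SAP*

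**What the plan says.** **Power and sample size calculation.** The text under Hypothesis states: "The primary outcome of this study is the frequency of social interactions measured via the Extent of Participation subscale of the CRIS". The same section says that "the sample size calculations are based on a t-test for comparisons of mean change" from pre- to post-intervention in a CRIS subscale. The level is 0.05 two-sided, the effect size 0.71, the SD 7, and 44 per group are to be evaluable. "After adjustment for 20% loss to follow-up, we will recruit 55 subjects in each group of this study". The text on the recruitment assessment, within the intervention development section, also calls the CRIS the primary measure, without naming a subscale. Table 2 shows that the CRIS has three scales.

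**SAP, Overview.** "The primary outcome will be the change in the three major types of parameters from pre- to post-intervention". The first type is community integration, including education and employment. The second is individual characteristics: PTSD, TBI self-efficacy, emotional status, coping, real-world tasks, resilience and life satisfaction. The third is neuropsychological. No rule combines them. The Overview continues: "Dependent variables will include TBI-self-efficacy, community integration indices, educational or work attainment as defined by the ICF qualifiers, and life satisfaction". On testing it says: "The basic testing of the hypotheses will involve ANOVA test and repeated measures ANOVA test". The next sentence reads: "Bonferroni adjustments will be made to account for multiple testing".

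**SAP, Hypothesis 1.** This section plans an ANOVA of pre-to-post change between the groups and names no outcome in that sentence. For the repeated-measures ANOVA, the dependent variables it names include TBI self-efficacy and real-world task performance. The MANCOVA concentrates on TBI self-efficacy. A linear mixed model (LMM) appears three times: twice without condition, the second time with baseline as a covariate, and once as the method to use when data are missing.

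**The concern.** Both descriptions of the primary outcome are current text in the same combined document. Someone working from the power section would test one CRIS subscale. Someone working from the SAP would have a broad set of measures, a Bonferroni rule with no scope, and several analyses (ANOVA, repeated-measures ANOVA, Friedman, MANCOVA, LMM) with none marked as deciding. The choice of outcome, alpha and model could then be settled after results are known.

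The alpha matters because the sample size was justified for one test at 0.05. If Bonferroni reaches that test, the stated 90% no longer describes the t-test or ANOVA of change on which the calculation rests.

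**Working it through.** **Inputs from the power section:** effect size d = 0.71, SD 7, two-sided alpha 0.05, 44 evaluable per arm, 20% loss.

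**1. The plan's own figure.** For a two-sample t-test with n per arm, the degrees of freedom are 2n − 2 and the noncentrality is d × √(n/2).
- At n = 44: 86 df, noncentrality 0.71 × √22 = 3.330, critical t 1.988, power 90.9%.
- The smallest n giving 90% is 43 per arm, so 44 is consistent with the plan.
- Loss: 44 / 0.8 = 55 per arm, 110 in total, as stated.
- The 0.71 must be standardised (0.71 × 7 = 4.97 points). Read as raw points with SD 7, it would need 2,043 per arm.
- The two-group ANOVA of change is the same test (F = t²) and has the same power.

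The figure therefore reproduces as one test at 0.05, with no multiplicity allowance.

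**2. If Bonferroni covered the CRIS test.** Alpha becomes 0.05/k. The documents give no k, so three readings of their own lists are used, counting one test per item:
- k = 2: the two outcomes in Study Hypothesis 1
- k = 3: the three parameter types
- k = 4: the four dependent variables in the Overview

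| k | alpha | critical t | power at 44 per arm | evaluable per arm for 90% | recruited per arm (÷ 0.8, rounded up) |
|---|---|---|---|---|---|
| 1 | 0.05 | 1.988 | 90.9% | 43 | 54 |
| 2 | 0.025 | 2.281 | 85.1% | 51 | 64 |
| 3 | 0.0167 | 2.442 | 81.1% | 56 | 70 |
| 4 | 0.0125 | 2.551 | 78.0% | 59 | 74 |

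The plan has 44 evaluable and 55 recruited per arm.

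**3. With the baseline value as covariate.** Assume SD 7 is the SD of change, with equal variances at both times and baseline-outcome correlation r. The residual variance divided by the change-score variance is (1 + r)/2, so the effective d is 0.71 × √(2/(1 + r)), with 85 df. At r = 0.5 this is 0.820; at r = 0.8 it is 0.748. The range of r is an assumption.

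| alpha | r = 0.5 | r = 0.6 | r = 0.7 | r = 0.8 |
|---|---|---|---|---|
| 0.05 | 96.7% | 95.7% | 94.6% | 93.5% |
| 0.025 | 93.9% | 92.3% | 90.6% | 88.8% |
| 0.0167 | 91.7% | 89.7% | 87.6% | 85.5% |
| 0.0125 | 89.9% | 87.6% | 85.3% | 82.8% |

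A smaller alpha therefore does not always bring power below 90%.

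**4. Which planned analysis could decide.** A change score needs a T2 value. The Missing Data section rules out imputing outcomes, so an ANOVA of change uses complete cases only. The same section links complete-case analysis to data missing completely at random, and warns that dropout may be informative. The SAP's Hypothesis 1 section calls for an LMM when data are missing, and the power section expects 20% loss. On the plan's own terms, the LMM condition will be met.

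**The case against.** The strongest reply is that only one overview sentence is out of line. The power section names the primary outcome plainly, and the looser references to the CRIS elsewhere can be read as shorthand for it. Community integration is one of the three types, the pre-to-post window agrees, and the ANOVA of change sits under a heading about community re-integration. This shows that the intended primary can be guessed. It does not remove the conflict: the SAP sentence does not limit the primary to the CRIS, and the outcomes that section names for its repeated-measures ANOVA and MANCOVA do not include it.

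A second reply is that every k here is assumed. That stands. Each type holds several measures, so one test per type is only one count. Because the Bonferroni sentence directly follows the one on repeated-measures ANOVA, it might refer only to comparisons among time points. The power loss is therefore conditional.

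Three stronger readings are tempting and are not supported:
- **That the trial is underpowered.** At 0.05 the stated 90% holds, and it is unaffected if Bonferroni covers secondary tests only.
- **That 90% holds only at 0.05.** That is true of the t-test or ANOVA of change at this sample size and effect. The SAP also plans baseline as a covariate, and step 3 shows 90% or more at smaller alphas in some cases.
- **That the ANOVA of change should decide because it matches the sample-size test.** It does match, but with 20% loss it would make the primary a complete-case analysis, against the plan's rule of using an LMM when data are missing.

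**Conclusion.** The point holds and should be corrected before any comparison of the arms. The document gives two incompatible statements of the primary outcome, a Bonferroni rule without scope, and no deciding analysis. The sample size supports one primary test at 0.05 and contains no allowance for more.

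The cost in power is conditional: 85.1%, 81.1% or 78.0% for k = 2, 3 or 4 with the t-test or ANOVA of change, if Bonferroni covers the CRIS test, and none if it does not. These figures rest on d = 0.71, 44 evaluable per arm, SD 7 as the SD of change, and the assumed k; the baseline-adjusted figures also rest on the assumed r. Using the full 0.05 at the end further assumes that the interim analysis planned at 13 months does not test the arms on this outcome.

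A reader might infer that the outcome will be picked after the fact. The documents do not show that; they only leave it possible.

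**What to change.** 1. **SAP, Overview, primary outcome.** Replace the sentence with: *The single primary outcome is the change in CRIS Extent of Participation from T1 to T2, tested at two-sided 0.05.* This matches the power section.
2. **SAP, Overview, multiplicity.** Replace the Bonferroni sentence with: *Bonferroni applies only within the secondary family listed here*, and list that family with its k. It should include TBI self-efficacy; the other dependent variables named in the Overview are the natural remaining members. Mark TBI self-efficacy as secondary in Study Hypothesis 1 and in the SAP's Hypothesis 1 analyses. If the sponsor prefers several primaries, list them, state k and restate the power.
3. **SAP, Hypothesis 1.** Name one deciding analysis that respects the missing-data rule. One example is the LMM already planned there, with the baseline value as covariate, using all available data and testing the group difference at T2. With baseline in the model, the group effect is the same whether the response is the T2 score or the change. Keep the ANOVA of change, on complete cases, as supportive. The LMM does not by itself deal with informative dropout.

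**Cost.** No extra patients: at 0.05, 44 evaluable per arm gives 90.9% with the ANOVA of change. A simple baseline-adjusted model at that number gives 96.7% to 93.5% for r from 0.5 to 0.8, which is a guide to the LMM rather than its exact power. The price is in content: TBI self-efficacy and the other listed dependent variables become secondary. Item 3 is also a real choice of method that the sponsor must make.

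### Single-step Bonferroni is valid, but Holm's step-down procedure gives the same family-wise error guarantee and can add power for the second and later outcomes

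*Combined protocol and SAP*

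**What the plan says.** The Overview of the Statistical Analysis Plan says that the basic hypothesis tests will be ANOVA and repeated measures ANOVA, and then: "Bonferroni adjustments will be made to account for multiple testing". It does not say which tests form the family, how many there are, or what per-test level results. It mentions no stepwise method and gives no reason for the single-step form.

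How many tests are adjusted depends on which part of the document is read:

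- The power section names one outcome: "The primary outcome of this study is the frequency of social interactions measured via the Extent of Participation subscale of the CRIS".
- The SAP Overview names more: "The primary outcome will be the change in the three major types of parameters from pre- to post-intervention".
- Study Hypothesis 1 claims benefit in two domains, TBI self-efficacy and community integration.

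The sample size rests on one test at the full level, "using a two-sided t-test with assumption of normality". The stated target is "90% power to test an effect size of 0.71 with a SD of 7 for difference in CRIS subscale score between groups", with 44 evaluable per group.

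**The concern.** For a family of k tests, single-step Bonferroni compares every p-value with 0.05/k. Holm orders the p-values and compares the smallest with 0.05/k, the next with 0.05/(k-1), and so on up to 0.05, stopping at the first failure. Both procedures hold the family-wise error at or below 0.05 whatever the dependence between outcomes. Every Bonferroni rejection is also a Holm rejection, but not the reverse.

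The plan intends claims on several outcomes with about 44 evaluable Veterans per arm. At that size, the stricter threshold on the second and third outcomes can decide whether a real effect there is declared. Where that happens, the power is given up with no stronger family-wise error guarantee in return.

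**Working it through.** **Inputs from the documents.** Two-sided 0.05, standardised effect d = 0.71, 44 evaluable per group, 20% loss (power section). **Assumed, because the documents do not give them:** the number of tests k, the effects on outcomes other than the CRIS subscale, and the correlation between outcomes.

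**Step 1: reproduce the plan's figure.** For a two-sample t-test with n = 44 per group, the degrees of freedom are 2 × 44 - 2 = 86 and the noncentrality is 0.71 × √(44/2) = 3.33. Power at 0.05 is 90.9%; 43 per group is the smallest size reaching 90%. Recruitment is 44/(1 - 0.20) = 55 per group, 110 in total. The stated sample size therefore reproduces for one test at 0.05. (The 0.71 has to be standardised, about 0.71 × 7 = 4.97 points. Read as raw points on an SD of 7, it would need 2043 per group.)

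**Step 2: per-test power under Bonferroni at 44 per group, exact t.**

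| k | Level 0.05/k | Power at d = 0.71 | Evaluable per group for 90% |
|---|---|---|---|
| 1 | 0.05 | 90.9% | 43 |
| 2 | 0.025 | 85.1% | 51 |
| 3 | 0.0167 | 81.1% | 56 |
| 5 | 0.01 | 75.5% | 61 |

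**Step 3: where Holm differs.** With k = 3 the Holm thresholds are 0.05/3 = 0.0167, 0.05/2 = 0.025 and 0.05. The first is the same as Bonferroni's. Only an outcome with a p-value between 0.0167 and 0.05 can gain, and only if every smaller p-value has already passed its own threshold.

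**Step 4: size of the difference.** Correlated two-sided t-statistics were simulated at 44 per group, with at least 200,000 replicates per scenario. Real effects have d = 0.71. Average power is per real effect.

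| Assumed family | Correlation | Average power, Bonferroni to Holm | All real effects detected, Bonferroni to Holm |
|---|---|---|---|
| 2 tests, both real | 0.3-0.5 | 0.85 to 0.89-0.90 | 0.74-0.76 to 0.83-0.84 |
| 3 tests, all real | 0.3-0.5 | 0.81 to 0.88 | 0.58-0.63 to 0.76-0.79 |
| 3 tests, two real | 0.3-0.5 | 0.81 to 0.84 | 0.68-0.70 to 0.74-0.76 |
| 3 tests, one real | 0.3-0.5 | gain about 0.001-0.002 | same |
| 5 tests, all real | 0-0.5 | 0.75 to 0.85-0.87 | 0.25-0.43 to 0.59-0.70 |
| 1 test | n/a | no difference | no difference |

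The chance of at least one rejection is identical under both methods. With three real effects it is 99.3% at correlation 0 and 95.5% at 0.5.

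**Step 5: error control.** With no real effects, the simulated family-wise error is the same for both methods, 4.2% to 5.0%. With one real effect among three at correlation 0, it is 3.3% under Bonferroni and 4.6% under Holm. Holm uses more of the allowance but stays within it.

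**The case against.** Four objections carry weight.

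- **Bonferroni is valid and prespecified.** A reader might infer that the plan fails to control type I error. It does not; this is a matter of efficiency only.
- **The largest gains need several real effects of 0.71.** The power section gives that figure for one CRIS subscale, and no effect is stated for self-efficacy or the neuropsychological measures. A reader might infer that real effects are being missed for nothing. The documents do not support that: the first rejection is equally likely under both methods, the gain nearly vanishes if only one effect is real, and Bonferroni offers simple matching simultaneous confidence intervals. The plan does not call for such intervals, so that advantage is small here.
- **The powered comparison may be untouched.** If the Extent of Participation subscale is tested alone at 0.05, Holm and Bonferroni coincide for it. A reader might take the 81% in Step 2 as the power of the primary test; that holds only if the test sits inside a family of three.
- **The family is undefined.** Because the sentence follows the mention of ANOVA and repeated measures ANOVA, it could refer to comparisons within those models rather than to several outcomes. Neither method can be applied until the family is fixed, and that gap is the larger problem.

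The last objection limits how precisely the benefit can be stated, but does not remove the point. For any family of two or more, Holm rejects at least as much at the same guaranteed level, and both Hypothesis 1 and the SAP Overview plan claims on more than one outcome.

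**Conclusion.** The point holds as a minor, cheap improvement. Bonferroni is not an error. Holm keeps the same family-wise guarantee under any dependence and can help with the second and later rejections. How much it helps here cannot be derived from the documents: for three tests, the scenarios checked run from next to nothing to about 0.07 in average power, and the upper end requires all three effects to be real at 0.71.

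**What to change.** Replace the sentence in the SAP Overview with: *Holm's step-down procedure will be used to control the family-wise error rate at two-sided 0.05 within each family of tests.* For the sentence to be operable, the SAP should also list the tests in each family and say whether the CRIS Extent of Participation comparison is inside one or stands alone at 0.05. That means reconciling the two statements of the primary outcome.

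The change needs no extra participants or data and should be made before any comparison by arm. Its one drawback is that simultaneous confidence intervals matching Holm are less simple than Bonferroni intervals; unadjusted 95% intervals can be shown alongside the adjusted tests and labelled as such.
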